8. SAFETY

8.1. Definitions Adverse Events

8.1.1. Adverse events (AE)

Adverse Event (AE): Any untoward medical occurrence in a clinical investigation subject administered a medicinal product and, which does not necessarily have a causal relationship with the treatment, can be an unfavorable and unintended sign (including an abnormal laboratory discovery), symptom or disease temporally associated with the use of the medicinal (investigational) product, in this trial being the weight vest. This whether or not the medical occurrence is related to the medicinal (investigational) product.

If an adverse event occurs the study subject can abort the study whenever he or she wants to. The medical personnel involved in the study will help the subject to the correct medical care giver practice if needs arise. Adverse events will be reported in the publication.

8.1.2. Serious Adverse events (SAE)

Serious adverse event (SAE): Any untoward medical occurrence that at any dose:

- results in death
- is life-threatening
- requires inpatient hospitalization or prolongation of existing hospitalization
- results in persistent or significant disability or incapacity
- results in a congenital anomaly/malformation

Study code: ATLAS

Version No: 14.9

Date: 2021-02-01

8.2. Assessment of Adverse Events

8.2.1. Assessment of casual relationship

The PI is responsible for determining whether there is a causal relationship between the AE/SAE and use of the investigational product, i.e., the weight vest.

Those AEs which are suspected of having a relationship to the investigational product will be followed up until the subject has recovered, is well taken care of and on their way to good recovery or until the state of the AE have become persistent (see also section 8.4, Follow-up of Adverse Events).

All AE will be categorized either as likely related, possibly related, or not related, in accordance with the definitions below:

Likely related: Clinical event, including abnormal results from laboratory analyses, occurring within a reasonable time after administration of the intervention/investigational product. It is unlikely that the event can be attributed to underlying disease or other medications but is most likely caused by the investigational product and its emergence is reasonable in relationship with use of the investigational product.

Possibly related: Clinical event, including abnormal results from laboratory analyses, occurring within a reasonable time after administration of the intervention/investigational product. The event could be explained by the investigational product and its emergence is reasonable in relationship with use of the investigational product, but there is insufficient information to determine the relationship. The event could be explained by an underlying disease or other medications.

Not related: Clinical event, including abnormal results from laboratory analyses, that is not reasonably related to the use of the intervention/investigational product. The event is unlikely related to the intervention/investigational product and can be explained by other medications or underlying disease.

8.2.2. Assessment of intensity

Each adverse event shall be classified by an investigator as mild, moderate or severe.

Mild: The adverse event is relatively tolerable and transient in nature but does not affect the subject's normal life.

Moderate: The adverse event causes deterioration of function but does not affect health. The event can be sufficiently unpleasant and interferes with normal activities but does not completely obstruct them.

Severe: The adverse event causes deterioration of function or work ability or poses a health risk to the subject.

8.2.3. Assessment of seriousness

The investigator is responsible for assessing the seriousness (serious or non-serious). If the incident is considered serious, this should be reported as a serious adverse event (SAE) by the investigator to the PI. See also section 8.3.2, Reporting of Serious Adverse Events (SAE).

Study code: ATLAS
Version No: 14.9

Date: 2021-02-01

8.3. Reporting and registration of Adverse Events

At each study visit, adverse events (AE) are registered, starting after a signed informed consent form (ICF) up to and including 2 weeks after the subject has ended their treatment with the weight vest. All AE that occurs during the study and which are observed by the investigator/study nurse or reported by the subject will be registered in an AE log and in the CRF regardless of whether they are related to the weight vest or not. Assessment of causal relationship, severity, and whether the AE is an SAE or not will be done by the investigator in an AE log and in the CRF. At minimum, for each AE/SAE, a description of the event is recorded (diagnosis/symptom if diagnosis is missing), start and stop dates, causal relationship, severity, if the AE is an SAE or not, measures and outcome. Follow-up information should be provided as necessary.

It will be left to the Investigator's clinical judgment to decide whether an AE is of sufficient severity to require the participant's removal from treatment. A subject may also voluntarily withdraw from treatment due to what he or she perceives as an intolerable AE. If either of these occurs, the participant must undergo an end of trial assessment and be given appropriate care under medical supervision until symptoms cease, or the condition becomes stable.

8.3.1. Reporting of Adverse Events (AE)

All AE shall be registered in the CRF within 2 workdays as above (section 8.3, Reporting and registration of Adverse Events).

8.3.2. Reporting of Serious Adverse Events (SAE)

Serious adverse events (SAE) are reported to the sponsor on a special SAE form which will be sent via mail within 24 hours of the investigator being informed of the SAE. Follow-up information describing the outcome and handling of the SAE is reported within 24 hours after this information is available. The original should be kept in the Investigator Site File (ISF). All SAE will be registered in an AE log and in the CRF.

8.4. Follow-up of Adverse Events

Adverse events will be monitored from screening to the last visit of the study. Follow-up will be done by study personnel at every study specific visit. Follow-up of the adverse event during the study will be done until the event is resolved, stable or have become persistent. Unacceptable adverse events, as judged by the investigator, can lead to withdrawal of the participant from the study. Any still ongoing adverse events at the end of the study will be reviewed by the investigator to determine appropriate follow-up.

8.5. Procedures in case of emergencies or pregnancy

The PI and investigator are obliged to immediately take the urgent safety measures necessary to protect the subjects from immediate danger. Examples of such measures are to temporarily suspend the clinical trial or to introduce supplementary monitoring measures. The PI shall inform Swedish Ethical Review Authority (Etikprövningsmyndigheten (EPM)) as soon as possible about the urgent safety measures taken by the investigator or PI.

Pregnancy is reported to the sponsor on a special pregnancy form which will be sent via mail within 24 hours of the investigator being informed of the pregnancy. Follow-up information describing the outcome (continuation of pregnancy, abortion or miscarriage) and handling of the pregnancy is reported within 24 hours after this information is available. The original should be kept in the Investigator Site File (ISF). Pregnancy will lead to withdrawal from the study due to safety reasons. Pregnancy will be registered in the CRF.

Study code:
Clinical Study Protocol

Version No:

Version No: 14.9

Date: 2021-02-01

ATLAS

The carrying of a weight vest is judged to be associated with low and few risks for the subjects. As judged by the research group the risk for congenital malformation on an eventual fetus/child if a subject is to be pregnant is very low. Due to this low risk of congenital complications an eventual pregnancy will be followed until the end of the study and necessarily not until birth has taken place. Any still ongoing pregnancy at the end of the study will be reviewed by the investigator to determine need of any further follow-up.

9. STATISTICS

9.1. Analysis population

The aim of this trial is to further elucidate the effect increased artificial loading has on body weight. It is important to identify if there is any effect of increased loading on obese subjects under optimal conditions and if all subjects are fully compliant to the study protocol. Therefore all participants that complete the study with regards to the primary outcome will be included in the analysis, e.g. analyses applicable to Full Analysis Set (FAS). A secondary per protocol analysis may be performed with regards to the study endpoints.

9.2. Statistical analyses

9.2.1. Statistical methods

The primary endpoint of this randomized study will be the change in body weight at the end of the intervention (day 35) expressed as percent of original body weight at day 0, i.e. the day of the start of the intervention. The values will be calculated for all individuals participating in the study. The values will then be compared between the groups of individuals exposed of 11% and 1% of artificial loading, using ANCOVA (assuming normality).

- An analysis of covariance (ANCOVA) using age, BMI at the start of the study, sex, time per day wearing the west (hours/day), and percent of the vest bearing time standing up as covariates will be performed.
- Non-parametric analysis will be performed if data cannot be assumed normally distributed even after transformation.

The secondary endpoints of this study are found under section 3.2 in the study protocol. All the secondary endpoints are regarded as exploratory endpoints. A selection of the secondary endpoints includes change in:

- Body weight at day 15 and day 28 expressed as absolute (g) and relative (% of baseline value) change compared to baseline.
- Abdominal, visceral and subcutaneous fat at day 35 (end of intervention) expressed as absolute (g) and relative (% of baseline value) change compared to baseline.
- Fat free mass and fat mass at day 15, day 28 and day 35 expressed as absolute (g) and relative (% of baseline value) change compared to baseline.
- Energy expenditure during intervention (day 14-28) expressed as absolute (Joule per day) and relative (% of baseline value) change compared to baseline (day -14 to day 0).
- Physical activity during intervention (day 15-21) expressed as absolute (time distribution in a spectrum of physical activity intensities) and relative (% of baseline value) change compared to baseline (day -13 to -7).
- Waist circumference at day 15, day 28 and day 35 expressed as absolute (cm) and relative (% of baseline value) change compared to baseline (day 0).
- Heart rate variability (HRV) during intervention (day 15) expressed as absolute (frequency) and relative (% of baseline value) change compared to baseline.

Study code: ATLAS
Clinical Study Protocol Version No: 14.9
Date: 2021-02-01

- Serum concentration at day 15 and day 35 of circulating proteins, metabolites or electrolytes compared to baseline.

- Analysis at day 15 and day 35 of proteomics or metabolomics compared to baseline.

These will be analyzed using the same methods as described for the primary endpoint. We will also compare absolute changes between the groups of individuals exposed to 11% and 1% artificial loading.

From the ANCOVA models adjusted for covariates, least square means (LSM) with 95 % confidence intervals will be calculated. P-values < 0.05 will be classified as significant. The p-values for within group comparison (5 weeks vs baseline) of the different parameters will be calculated using Wilcoxon signed rank-sum test.

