2.3. Risk/Benefit evaluation

In general, this is a study with few risks. The weight vests used in this experiment are daily used by thousands of people for exercise. During previous experiments on 72 subjects for three weeks no serious adverse events were reported. In the high load group, there was a higher reporting of musculoskeletal adverse events (1 person experienced arthralgia, 2 myalgia, 2 pain in lower extremity, 2 swelling of ankle and/or foot). This is contrasted to 1 person experiencing musculoskeletal adverse events in the low load group (1 myalgia). However, only one subject from the high load group and one subject from the low load group discontinued the study due to musculoskeletal adverse events. It is probable that the musculoskeletal adverse events are due to increased axial loading. However, it should be noted that the risks of wearing a weight vest for several weeks in a row are largely unknown. No serious adverse event was reported in any of the treatment groups. [1]

To minimize the risks we have decided to include only healthy obese subjects consuming no or few medications. The trial will include availability of medically trained personnel, such as physicians and experienced nurses. The trial is to be performed at the Sahlgrenska University Hospital. Study subjects are allowed to withdraw their participation from the study at any time.

Blood sampling can be experienced as somewhat uncomfortable by a few individuals. However, it is generally free from complications. In some subjects, there may be small local bruising or inflammation. We may fail to get venous blood from 5-10% of these obese subjects which may cause some additional suffering and increase the risk of complications.

We plan to perform CT-scans and Dual-energy X-ray absorptiometry (DXA) on two separate occasions for measurement of visceral fat, liver fat and body composition at baseline and after 5 weeks. These procedures will entail exposure to a small dose of radiation. Possible unexpected abnormal findings during the CT- or DXA-scans will be investigated and followed up according to the treatment recommendations at the Sahlgrenska University Hospital.

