6.1. Randomization

Subjects are included consecutively as they are found to be eligible for inclusion in the study. After the baseline period at day 0 subjects will be randomized in a 1:1 ratio into either the high load group (heavy weight vest) or the low load group (light weight vest). Randomization will be through permuted blocks, stratified by age 18-50 years, age 51-65 years and gender. It will be performed in the Case Report Form (eCRF) using a built-in function for the purpose. If a subject discontinues their study participation, their randomization code will not be reused and the subject will not be allowed to reenter the study again.

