7.1.2.11. Weight vest diary

All subjects will at the start of intervention on day 0 be given a diary for daily registration of number of hours wearing the weight vest. In the diary the subject is to register time wearing the weight vest and number of hours standing during the day with the weight vest. This diary is to be recorded for each day during intervention (day 0 to day 35) and thereafter to be returned to the study personnel at the study center. Data from this diary will calculate deviation from the mandatory vest wearing time of 8 hours per day as a mean of the total vest wearing time for all 5 intervention weeks, this at the end of the intervention (day 35). It will likewise calculate a subject's time in a standing position. Participants will be encouraged to use the vest standing > 2 hours per day. The full diary can be found in attachments 17.4.

Study code: ATLAS
Version No: 14.9

Date: 2021-02-01

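### The primary ANCOVA adjusts for vest-wearing hours and share of time standing, both self-reported after randomisation, so its group difference need not estimate the effect of assigned load and can be biased

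*Protocol*

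**What the plan says.** Section 9.2.1 names the primary test, "using ANCOVA (assuming normality"), for percent change in body weight from day 0 to day 35. It gives one covariate list. Age and baseline BMI come first, and the remaining entries read "sex, time per day wearing the west (hours/day), and percent of the vest bearing time standing up as covariates will be performed". It then says which model supplies the reported results: "From the ANCOVA models adjusted for covariates, least square means (LSM) with 95 % confidence intervals will be calculated". The secondary endpoints follow the same methods. No model restricted to baseline covariates is given.

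The timing is clear elsewhere in the protocol:

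- Section 6.1: "After the baseline period at day 0 subjects will be randomized in a 1:1 ratio". Vest wearing starts directly afterwards (section 4.4.7).
- Section 7.1.2.11: at day 0 participants will "be given a diary for daily registration of number of hours wearing the weight vest", and the same diary takes standing time. "This diary is to be recorded for each day during intervention (day 0 to day 35").
- Section 9.2.2: both totals are worked out after day 35 from self-report.

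Two further passages bear on whether load could alter these variables. On the earlier three-week study, section 2.3 states: "In the high load group, there was a higher reporting of musculoskeletal adverse events". Section 4.1 sets a floor of 2 h/day standing in the vest, sets no ceiling, and encourages more.

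**The concern.** Randomisation makes the arms comparable at day 0. Adjusting for variables fixed by then keeps that comparability and can add precision. Adjusting for what happens afterwards can lose it, in two ways.

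First, if load changes how long people wear the vest or stand, and wearing or standing affects weight, the adjustment removes that part of the effect. The model then answers how the arms would compare at equal wearing and standing time, not what assignment to the heavy vest does.

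Second, if an unmeasured trait such as motivation drives both the diary entries and weight change, conditioning on the entries creates an association between arm and motivation that randomisation had excluded. An apparent effect can then arise when there is none.

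Self-report adds to this. An 11% vest is unlikely to be mistaken for a 1% vest, and section 4.1 says participants are told of the weight-loss hypothesis, so reporting itself may differ by arm.

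At stake is the trial's only confirmatory test, since section 9.2.1 treats all secondary endpoints as exploratory.

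**Working it through.** **1. The plan's own figure.** Section 9.3 gives a difference of 1.6 points, SD 2%, alpha 0.05 (taken as two-sided) and 80% power. Then n per arm = 2 × (1.960 + 0.842)² × (2/1.6)² = 24.5, so 25, as stated. Power at 25 per arm is 80.7% by the normal formula and 79.1% by the t-test. No covariate enters this calculation.

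**2. General form of the distortion.** With one post-randomisation covariate W:

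adjusted difference = unadjusted difference − (within-arm slope of outcome on W) × (mean W in high load − mean W in low load).

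The two estimates agree if the arms do not differ in W, or if W is unrelated to weight change within arm. Otherwise they differ, and the sign depends on both factors. The protocol reports neither factor, for wearing or for standing.

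**3. Illustration with no true effect (inputs assumed except 25 per arm and SD 2).** Let T = 1 for high load, U a standardised unmeasured trait, and δ the shortfall in wearing hours in the heavy arm:

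- W = 8 − δT + 0.7U + 0.7e, so the within-arm variance is 0.49 + 0.49 = 0.98 (SD about 1 h).
- Weight change = −gU + noise, total SD 2. With g = 0.5 or 1.0, U explains g²/4 = 6% or 25% of the variance.
- Within-arm slope = −0.7g/0.98 = −0.714g.
- Adjusted difference = 0 − (−0.714g)(−δ) = −0.714gδ.
- Residual variance = 4 − 0.5g²; variance inflation = 1 + δ²/(4 × 0.98).
- SE = √(residual variance × 2/25 × inflation).

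| δ (h/day) | g | Adjusted estimate | SE | Type I error (noncentral t, 47 df) |
|---|---|---|---|---|
| 0.5 | 0.5 | −0.18 | 0.574 | 6.1% |
| 0.5 | 1.0 | −0.36 | 0.546 | 9.8% |
| 1 | 0.5 | −0.36 | 0.624 | 8.7% |
| 1 | 1.0 | −0.71 | 0.593 | 21.9% |

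Simulation of the same model (5,000 trials per cell) gave 8.3–22.3% for a 1 h gap and 6.4–9.5% for 0.5 h, while the unadjusted test stayed at 4.7–5.2% for the 1 h gap. A second simulation with other inputs (trait correlated 0.5 with wearing and worth 1 point per SD, heavy arm 1 SD lower) gave −0.51 points and 12.8%.

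**4. With a true effect.** Under the 1 h gap of step 3, a true −1.6 reads as −1.6 − 0.36 = −1.96 up to −1.6 − 0.71 = −2.31. If wearing itself lowers weight by 0.5 point per SD and the heavy arm wears 1 SD less, the total effect of assignment is −1.6 + 0.5 = −1.1. The adjusted model returns −1.6 with no shared cause, and −2.11 with one.

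**5. Cost without bias.** If wearing is unrelated to weight but the arms differ by 1 SD, variance inflation is 1/(1 − 0.2) = 1.25. With 50 participants and seven parameters (43 df), power falls from 79% (noncentrality 2.83) to 70% (2.83/√1.25 = 2.53).

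**6. Control case.** With no arm difference in wearing, both models are unbiased: −1.60 each under the alternative, and type I error 5.1% unadjusted and 5.2% adjusted under the null.

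**The case against.** **The adjustment may be deliberate.** Section 9.1 voices interest in the effect under optimal conditions with full compliance. That does not justify the model. Least-squares means are ordinarily evaluated at average covariate values, not at full compliance. Reading an adjusted contrast as a compliance effect also requires that nothing unmeasured drives both compliance and weight. Section 9.1 itself keeps the primary analysis on all who complete for the primary outcome, and a possible per-protocol analysis is provided separately.

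**The covariate list may describe a second analysis.** On that reading the first ANCOVA has no stated covariates, and the reported means and intervals still come from the adjusted models.

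**The inputs are assumed, and all point one way.** This stands. Section 2.3 also records equal discontinuation for musculoskeletal events, one per arm, and does not say that wearing time fell. Both arms are asked for 8 h/day. A mean of 7 h with SD 1 h would put about 27% of the heavy arm under the 6.4 h limit in section 5.3, so a 1 h gap is large. Sections 5.3 and 9.2.2 differ on whether such participants leave the study or stay in the primary set. If the heavy arm wore or stood more, the sign would reverse. Standing share was not simulated.

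**Two further inferences go beyond the text.** A reader might infer that a participant without a diary drops out of the primary model, but the protocol states no rule for missing covariates. A reader might also fault the absence of an arm-by-wearing interaction, a detail that a separate analysis plan may settle.

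**Conclusion.** The point holds as a defect in the stated primary model. Two variables that arise after randomisation are fixed as covariates in the only specified primary ANCOVA, so the reported difference need not be the effect of assignment. It can be biased, and its type I error can exceed 5%.

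A reader might go further and conclude that the estimate is biased, or that type I error is certainly not controlled. The protocol does not support that. Bias as an estimate of the assignment effect requires both an arm difference in wearing or standing (or in its reporting) and a within-arm relation to weight change. Sections 2.3 and 4.1 make an arm difference plausible but do not establish it. Nor is equal wearing and standing the only safe case, since a zero slope also removes the bias.

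The 8–22% (1 h gap) and 6–10% (0.5 h gap) figures show what moderate assumptions can produce. They are not estimates for this trial. The case for change does not rest on them: as written, the validity of the single confirmatory test depends on conditions that the design does not secure.

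**What to change.** In section 9.2.1, define the primary ANCOVA as arm plus pre-randomisation covariates only: age and sex, which are the stratification factors, and baseline BMI or body weight. Apply the same restriction to the secondary models that follow it, and take the least-squares means and intervals from these models.

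Report wearing hours and standing share descriptively by arm, or use them in a labelled exploratory compliance or dose-response analysis, for instance within the high-load arm, with its no-unmeasured-confounding assumption stated.

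The cost is a wording change. No new data are needed, and 25 per group stands because section 9.3 never used these covariates.

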9.3. Sample size calculation

It is anticipated that a total of approximately 130 subjects are required to be screened to identify a statically significant (p<0.05) effect of 1.6% difference in relative body weight change between 5 weeks and baseline, when comparing high load with the low load group with 80% power. These calculations will allow a screening failure of 50% and a dropout rate of 20% after screening. Calculations are based on a standard deviation of 2% for change in body weight comparing 5 weeks with baseline. Power calculations demonstrate that a total of 25 evaluable participants per group are needed to significantly detect above mentioned effect size with a power of 80%.

Subjects will be screened and included in the clinical trial consequently until 25 subjects in the heavy weight vest group (intervention/high load group) and 25 subjects in the light weight vest group (control/low load group) are certain to complete the trial and be eligible for Full Analysis Set (FAS). Certainty will occur when that number of subjects have finished the intervention on day 35. Eligibility to Full Analysis Set (FAS) is defined as having completed the study visits on randomization (day 0) and at the end of intervention (day 35) and thus being eligible for assessment of the primary outcome. Screening and inclusion will probably be executed according to above mentioned calculations but could be adjusted along the timeline of the trial.

Study code: ATLAS
Version No: 14.9

Date: 2021-02-01

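### The secondary-endpoint ANCOVAs omit the baseline value of the endpoint analysed, which costs some precision for the noisier exploratory endpoints

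*Protocol*

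**What the plan says.** Protocol section 9.2.1 compares percent change in body weight at day 35 between arms by ANCOVA. Four of the five covariates are given as "using age, BMI at the start of the study, sex, time per day wearing the west (hours/day"; the fifth is the share of vest time spent upright. The endpoint's own baseline value is not on this list.

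The section then names a selection of the secondary endpoints, including abdominal fat, body composition, energy expenditure, activity, waist, heart rate variability and serum markers. It states: "These will be analyzed using the same methods as described for the primary endpoint". The next sentence confirms that change scores are analysed: "We will also compare absolute changes between the groups of individuals exposed to 11% and 1% artificial loading". Results are reported from these models: "From the ANCOVA models adjusted for covariates, least square means (LSM) with 95 % confidence intervals will be calculated". On their status, the section says: "All the secondary endpoints are regarded as exploratory endpoints".

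No other section adds a baseline term. The baseline value enters only by subtraction or as the denominator of percent change.

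**The concern.** A change score is usually negatively related to its own baseline value: a participant who starts high by chance tends to fall. When baseline is not in the model, that variation stays in the residual and widens the confidence interval. With 25 evaluable participants per arm there is little precision to spare.

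BMI is the only size-related covariate, and section 5.1 restricts it to above 30 and at most 35. It is the same covariate for endpoints as different as gut hormones, spectral power of heart rate and reported calories. Randomisation is stratified only by age group and sex (section 6.1), so the design does not balance these baselines either. The trial already collects them before or around day 0 (sections 4.4.5, 4.4.7 and 7.1.2).

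**Working it through.** **The plan's own figure.** Section 9.3 assumes a difference of 1.6 percentage points and an SD of 2%, with p<0.05 and 80% power. Taking the test as two-sided, n per arm = 2(1.960 + 0.842)² × (2/1.6)² = 24.5, so 25. The stated number reproduces, and power at 25 per arm is 80.7% by the normal approximation. The calculation concerns body weight only; no secondary endpoint is powered.

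**Where the loss comes from.** Take equal variance s² at both visits and baseline-to-follow-up correlation ρ, with no other covariates:

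- Variance of the change score: 2(1−ρ)s²
- Residual variance after baseline adjustment: (1−ρ²)s²
- Ratio: (1+ρ)/2, which is 0.75, 0.85 and 0.95 at ρ = 0.5, 0.7 and 0.9

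These ratios compare with a model that has no covariates at all, which is not what the protocol plans.

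**Against a model with the planned number of covariates.** This was simulated with 4,000 trials per setting and 25 per arm. Each trial had a BMI variable correlated 0.3 with baseline and four further covariates drawn as noise, and was analysed with and without the endpoint's baseline value. The coefficient of variation was 20%. In the last row it was 12% and the BMI correlation 0.5, to resemble body weight. The protocol gives none of these values; all are assumptions.

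| Assumed ρ | Variance ratio, absolute change | Variance ratio, percent change | Participant equivalent (from absolute change) |
|---|---|---|---|
| 0.5 | 0.81 | 0.78 | 1/0.81 = 1.23, so 23% more |
| 0.7 | 0.89 | 0.87 | 1/0.89 = 1.12, so 12% more |
| 0.9 | 0.98 | 0.97 | 1/0.98 = 1.02, so 2% more |
| 0.99 | 1.02 | 1.02 | none |

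The standard error falls by 1 − √0.81 = 10%, 1 − √0.89 = 6% and 1 − √0.98 = 1% in the first three rows. Percent change does not remove the loss, because dividing by baseline is not the same as regressing on it.

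**The primary endpoint.** The input is "Calculations are based on a standard deviation of 2% for change in body weight comparing 5 weeks with baseline". Assume a coefficient of variation of body weight of 10 to 15%. Then ρ ≈ 1 − (2/10)²/2 = 0.98 to 1 − (2/15)²/2 = 0.99, and (1+ρ)/2 = 0.990 to 0.996. Estimating one more coefficient with 50 participants costs about 2%, which cancels a gain of at most 1%. The last row of the table shows this.

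**Chance imbalance is the same loss.** At ρ = 0.5, in units of s², the variance of the difference in mean change is 2(1−0.5) × 2/25 = 0.08. It splits into (1−0.25) × 2/25 = 0.06, which remains after adjustment, and (1−0.5)² × 2/25 = 0.02, which comes from baseline imbalance. The square root of 0.02 is 0.14 SD, the shift produced by a one-standard-error imbalance. It is already inside the 0.08 and must not be added to the variance loss.

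**The case against.** The strongest case against runs as follows. The affected endpoints are all labelled exploratory. The primary endpoint gains nothing. The models already contain age, BMI and sex. Every correlation used above is assumed. The covariate list is written for the primary endpoint, and the carry-over sentence follows what is called a selection of endpoints, so endpoint-specific terms might be set in a statistical analysis plan that is not shown.

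Most of this stands and limits the size of the point. It does not remove it. The protocol states an explicit list and extends the same methods to the secondary endpoints, so an analysis plan that followed the text would carry the omission forward. The exploratory results are still to be reported as adjusted means with 95% confidence intervals and judged against p < 0.05.

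A reader might infer three stronger claims that the document does not support:

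- **Bias from regression to the mean.** Under 1:1 randomisation it acts equally on both arms in expectation, so the comparison of change stays unbiased.
- **Lost power for the primary endpoint.** The protocol's own SD of 2% implies a correlation so high that there is nothing to recover.
- **A loss like 33%, 18% or 5% of participants.** These figures follow from (1+ρ)/2 but compare with a model without covariates.

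**Conclusion.** The omission is real and easily avoided. Its cost is precision only, including sensitivity to chance baseline imbalance, and no bias. For assumed correlations of 0.5 to 0.9 the avoidable share of the variance is about 19% down to 2%. The loss matters for endpoints with low to moderate correlation between visits, plausibly serum markers, heart rate variability, reported intake and activity. It is negligible for body weight, including the primary endpoint.

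The omission itself can be read directly from section 9.2.1. Its size rests on assumed correlations, equal variances at both visits and a BMI correlation of 0.3 with baseline. Because all affected endpoints are exploratory, this is a modest improvement and not a threat to the trial's main conclusion.

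**What to change.** In section 9.2.1, directly after "These will be analyzed using the same methods as described for the primary endpoint", add:

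> *with the baseline value of the endpoint analysed added as a covariate in each ANCOVA; where a transformation is used, the baseline value is transformed in the same way.*

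Baseline here should mean the pre-intervention value. For the day-49 endpoints in section 3.2, which measure change from day 35, the day-35 value is observed after randomisation and should not take its place.

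The cost is one degree of freedom per model and no new data. The stated absolute and percent change measures stay as they are. Whether BMI and the two adherence covariates, which are measured after randomisation, should remain in the model is a separate question that this change does not settle.
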